10.2. Analyses of Secondary Efficacy Endpoints

To control alpha, the Key Secondary Endpoint of Overall Survival (OS) will only be analyzed if the primary endpoint is statistically significant. The primary and key secondary endpoints are the only endpoints that will be controlled for alpha.

10.2.1. Key Secondary Endpoint

Overall survival (OS), defined as the time from randomization to death from any cause, will be calculated using randomization date and date of death, or date of last follow-up for censored subjects. Time to death is defined as the time between randomization and death from any cause. All subjects will be followed until drop-out, death, or study closure. Drop-out may be due to withdrawal of consent from further data collection or lost to follow-up. Subjects who drop-out or are alive at study closure (or at the time of the interim analysis [Section 15.2]) will have their OS times censored at the date of last known alive, as appropriate.

The analysis of OS will be performed using the ITT population for the interim and final analysis. The null hypothesis for testing the key secondary efficacy endpoint, time to death from any cause, is that the overall survival distributions for the two treatment groups are equivalent. Overall survival curves will be estimated using Kaplan-Meier (KM) methods and will be compared using a stratified log-rank test, stratifying by average baseline RBC transfusion requirement (≤ 4 units versus > 4 units of RBC per 28 days), baseline platelet transfusion status (dependent or independent) and ECOG performance status (0 to 1 versus 2). The p-value from the stratified log-rank test will be the confirmatory p-value. The p-value from the final analysis of the OS endpoint will be adjusted for the interim analysis to preserve the overall alpha level at 0.05 (see Section 15.2 for further details regarding the interim analysis and methods for controlling the overall alpha level). Kaplan-Meier estimates for median OS as well as the 25th and 75th percentiles and associated two-sided 95% CIs will be summarized for each treatment group, unadjusted for the stratification variables. In addition, both the numerical difference and the 95% CI of the difference, in the median, 25th, and 75th percentiles between the two treatment groups will be presented for the unstratified analysis. Plots of the KM survival curves will be presented for the two treatment groups, without adjustment for the stratification variables. At the time of the final OS analysis, a stratified Cox proportional hazards model will be used to estimate the corresponding hazard ratio and 95% CI for oral azacitidine relative to placebo. The stratification variables average baseline RBC transfusion requirement (≤ 4 units versus > 4 units of RBC per 28 days), baseline platelet transfusion status (dependent or independent) and ECOG performance status (0 to 1 versus 2), will be derived from the corresponding CRF pages and used in the stratified log-rank test and the stratified Cox proportional hazards model.

Additionally, KM methods will be used to estimate the 1-year and 2-year survival probabilities for time to death from any cause. Estimates of the 1-year (365 days) and 2-year (730 days) survival probabilities and corresponding 95% confidence intervals will be presented by treatment

group. Median follow-up time by treatment will be estimated using KM methods. The analysis of the OS endpoint will be repeated for the mITT population as a supportive analysis.

To assess the potentially confounding effects of other cancer therapy received subsequent to the protocol therapy on the survival estimates, a sensitivity analysis based on the ITT population, will be performed using modified censored criteria. For this analysis, subjects who received subsequent therapy for MDS following discontinuation from their protocol therapy will be censored on the date that the subsequent therapy was started regardless of their survival status at the time of the final analysis. This modified time-to-death endpoint will be analyzed using the same methods as described above for the key secondary efficacy analysis.

The supportive and sensitivity analyses for the OS endpoint will be performed only at the time of the final analysis of OS.

10.2.2. Platelet response (HI-P)

HI-P is defined according to IWG 2006 criteria ([Appendix E](#)). HI-P rates will be summarized and compared between the two treatment groups using the same methods as the primary endpoint (see [Section 10.1](#)). The response collected in the IWG MDS Response Criteria CRF, and the response derived using central labs per IWG criteria will be summarized and analyzed separately. The detailed derivation is provided in [Appendix F](#).

10.2.3. RBC transfusion independence for 84 days

RBC transfusion independence for 84 days is defined as the absence of any RBC transfusion during any consecutive “rolling” 84 days during the treatment period, i.e., Day 1 to 84, Day 2 to 85, Days 3 to 86, etc. The response is derived similarly as the derivation of the primary efficacy endpoint, except the rolling period is 84-day. The response of RBC transfusion independence for 84 days will be analyzed similarly as the RBC transfusion independence for 56 days ([Section 10.1](#)).

10.2.4. Duration of RBC transfusion independence of ≥ 56 days (8 weeks)

Duration of RBC transfusion independence will be analyzed only for subjects who achieve RBC transfusion independence of ≥ 56 days on treatment. Duration of RBC transfusion independence is defined as the time from the date transfusion independence is first observed (day 1 of a ≥ 56 days period without a transfusion) until the date the subject has a subsequently documented RBC transfusion. In case a subject has more than one ≥ 56 days rolling periods which meet the RBC independence criteria, the duration with the longest rolling period will be used in the analysis. Subjects who maintain RBC transfusion independence through the end of the treatment period or who are still on-going with the treatment will be censored at the end date of evaluation period which is defined in [Section 10.1](#). Duration of RBC transfusion independence curves will be estimated using KM methods and treatment groups will be compared using an unstratified log-rank test.

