10.6.2.2 Additional Secondary Efficacy Analyses

For secondary efficacy analyses, KM methods will be used to estimate curves for time to event secondary variables. Counts and percentages will be used to describe categorical secondary variables. Secondary efficacy analyses will be performed on the ITT population unless otherwise specified.

Platelet response (HI-P) is defined according to IWG 2006 criteria (Cheson, 2006; Appendix D). HI-P rates will be summarized and compared between the two treatment groups using the same methods as the primary endpoint (see Section 10.6.1).

RBC transfusion independence for 84 days is defined as the absence of any RBC transfusion during any consecutive “rolling” 84 days during the treatment period, ie, Day 1 to 84, Day 2 to 85, Days 3 to 86, etc. Frequency cross-tabulations of RBC transfusion dependency status for 84 days at baseline versus on-treatment will be presented by treatment group.

Duration of RBC transfusion independence for 56 days will be determined only for subjects who achieve RBC transfusion independence on treatment. Duration of RBC transfusion independence is defined as the time from the date transfusion independence is first observed (day 1 of 56 or more days without a transfusion) until the date the subject has a subsequently documented transfusion of RBC. Subjects who maintain RBC transfusion independence through the end of the treatment period will be censored at the date of treatment discontinuation or death, whichever occurs first. Duration of RBC transfusion independence curves will be estimated using KM methods and treatment groups will be compared using a log-rank test.

Time to RBC transfusion independence for 56 days is defined as the time between randomization and the date onset of transfusion independence is first observed (ie, Day 1 of 56 without any RBC transfusions). Subjects who do not achieve RBC transfusion independence during the treatment period will be censored at the date of treatment discontinuation or death, whichever occurs first. Time to RBC transfusion independence curves will be estimated using KM methods and treatment groups will be compared using a log-rank test. A Cox proportional hazards model will be used to estimate the corresponding hazard ratio and 95% CI.

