10.2.5. Time to RBC transfusion independence of ≥ 56 days (8 weeks)

Time to RBC transfusion independence of ≥ 56 days is defined as the time between randomization and the date onset of transfusion independence is first observed (ie, Day 1 of 56 without any RBC transfusions). Subjects who do not achieve RBC transfusion independence

during the treatment period will be censored at the end date of evaluation period which is defined in Section 10.1. In case a subject has more than one rolling periods which meet the independence criteria, the time to the first rolling period will be used in the analysis. Time to RBC transfusion independence curves will be estimated using KM methods and treatment groups will be compared using a stratified log-rank test. A stratified Cox proportional hazards model will be used to estimate the corresponding hazard ratio and 95% CI. Time to RBC transfusion independence (in month) for at least 56 days will also be summarized using descriptive statistics based on subjects who achieve the response.

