10.2.13. Duration of platelet transfusion independence

Duration of platelet transfusion independence will be analyzed only for subjects who are platelet transfusion dependent at baseline and achieve platelet transfusion independence on treatment. The calculation of the duration is similar as for the duration of RBC transfusion independence of ≥ 56 days (Section [10.2.4](#)), except using platelet transfusion. Duration of platelet transfusion independence will be analyzed descriptively using KM methods.

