16. CHANGES TO THE STATISTICAL ANALYSES SECTION OF THE PROTOCOL

As there were no subjects enrolled from Japanese sites, the randomization stratification factor “country of enrollment (ie, Japan versus ROW)” will not be used when the analysis is performed.

Frequency cross-tabulations of RBC transfusion dependent status for 84 days at baseline versus on treatment will not be provided.

The end date of the evaluation period defined in Section 10.1 is used as the censoring date when calculating the duration of RBC transfusion independence ≥ 56 days and ≥ 84 days, duration of RBC transfusion reduction and duration of platelet transfusion independence. As defined in Section 10.1, the days after a subject started subsequent MDS treatment will not be included in the response duration. The end date of the evaluation period defined in Section 10.1 is also used as the censoring date for subjects who do not achieve the corresponding response during the treatment period in the analysis of time to RBC transfusion independence ≥ 56 days and ≥ 84 days, and time to platelet transfusion independence.

Progression to AML will be identified based on documentations in central lab report or Follow-up Status CRF, please see detail in Section 10.2.8.

No other changes to the statistical analyses section of the protocol are made in this SAP.

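### SAP 10.2.4 defines duration of transfusion independence from its first onset but then analyses each responder's longest run, an undeclared departure that lengthens reported duration.

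*SAP*

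**What the plan says.** Protocol 10.6.2.2: "Duration of RBC transfusion independence is defined as the time from the date transfusion independence is first observed", running "until the date the subject has a subsequently documented transfusion of RBC". It is determined in responders only, and the arms are compared by a log-rank test.

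SAP 10.2.4 repeats the definition ("defined as the time from the date transfusion independence is first observed") and the restriction ("Duration of RBC transfusion independence will be analyzed only for subjects who achieve RBC transfusion independence of ≥ 56 days on treatment"). It then adds a rule for subjects with more than one qualifying period: "the duration with the longest rolling period will be used in the analysis". The arms are compared by an unstratified log-rank test.

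SAP 10.2.5, for time to independence in the same situation: "the time to the first rolling period will be used in the analysis".

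SAP 10.2.6 (84-day independence), 10.2.11 (RBC transfusion reduction) and 10.2.13 (platelet independence) calculate duration by reference to 10.2.4.

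SAP 16 declares a new censoring date for these same durations but does not mention the longest-run rule. It closes: "No other changes to the statistical analyses section of the protocol are made in this SAP".

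**The concern.** Two consecutive statements in SAP 10.2.4 give different answers for any responder who relapses to transfusion and later has a longer qualifying run. The definition points to the first run; the selection rule points to the longest. Reading the rule as a choice between overlapping windows within one run does not help: windows of fixed length are all equally long, so a longest one can exist only between separate runs.

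Three things are at stake.

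- **Traceability.** A reader relying on SAP 16 would take the reported duration to be the protocol's.
- **Coherence.** Onset (10.2.5) and duration (10.2.4) can describe different episodes in the same subject.
- **Interpretation.** The maximum of several runs grows with the number of runs a subject has time to accumulate. Reported duration then partly reflects how long subjects stayed on treatment.

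**Working it through.** **1. The plan's own figure.** The documents give no figure for duration. The nearest is the response-rate power (protocol 10.3, SAP 4.4): 108 per arm, two-sided alpha 0.05, un-pooled variance. Power = Φ(|p1 − p2| / √[(p1q1 + p2q2)/n] − 1.96).

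- 0.30 vs 0.05: √[(0.21 + 0.0475)/108] = 0.0488; 0.25/0.0488 − 1.96 ≈ 3.16; power 0.9992 (stated: about 99%).
- 0.15 vs 0.05: √[(0.1275 + 0.0475)/108] = 0.0403; 0.10/0.0403 − 1.96 ≈ 0.52; power 0.700 (stated: about 70%).

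Both reproduce. They imply the numbers entering the duration analysis: 108 × 0.30 = 32.4, 108 × 0.15 = 16.2 and 108 × 0.05 = 5.4. That is about 32 vs 5 responders, or 16 vs 5.

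**2. Direction.** A subject with runs of 60 and then 150 days has duration 60 from first onset and 150 under the selection rule. In general the longest run is never shorter than the first. A first run followed by another must have ended in a transfusion, so the rule replaces an event by a later event or a later censoring. With no censored durations between the old and new values, the KM curve can only stay the same or move up.

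Censoring in between allows a local exception. Take three responders: A (60 becoming 150, event), B (censored at 100) and C (event at 200). Between days 150 and 200 the first-run curve is at 2/3 and the longest-run curve at 1/2. The individual values still only lengthen.

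**3. Size.** This needs assumptions that are not in the documents: independent exponential gaps between transfusions, a qualifying run of at least 56 days, and the last run censored at end of treatment. Gap means of 20, 30, 45 and 60 days were crossed with 182, 364 and 728 days on treatment, with 10,000 subjects per setting. Four of the twelve settings:

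| Mean gap (days) | Days on treatment | Responders with >1 run | KM median, first run | KM median, longest run | Rise |
|---|---|---|---|---|---|
| 20 | 182 | 7% | 69.9 | 70.8 | 1% |
| 30 | 364 | 63% | 76.7 | 89.3 | 16% |
| 45 | 364 | 83% | 87.5 | 114.2 | 31% |
| 60 | 728 | 100% | 98.0 | 174.7 | 78% |

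The median rose in all twelve settings, and 3% to 77% of responders had their value changed. At a mean gap of 45 days and 182, 364 and 728 days on treatment, the first-run median was 87.5, 87.5 and 86.7 days. The longest-run median was 94.4, 114.2 and 144.3.

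These settings produced 39% to 100% responders, against planned rates of 30% (or 15%) and 5%. They show the mechanism and are not forecasts for this trial.

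**4. Between-arm comparison.** The same gap process was used in both arms (mean 30 or 45 days), with 32 vs 5 or 32 vs 16 responders and 800 trials per setting. Log-rank rejection at nominal 5%:

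- First run: 4% to 8%, whatever the treatment times.
- Longest run, equal treatment time: 5% to 8%.
- Longest run, one arm treated 2 to 4 times as long: 19% to 85% overall (20% to 64% at 32 vs 5).

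**The case against.** The protocol has no explicit rule for several qualifying runs, and the SAP sentence can be read as filling that gap. The longest run is also a legitimate summary in itself, biased only if the first run is the target. This has some force. But both documents state the start point as first observation, the SAP's companion endpoint takes the first run, and a gap-filling rule that changes the result still belongs in SAP 16.

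A reader might go further in four ways that the documents do not support.

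- **That the SAP introduced an invalid responder-only test.** Protocol 10.6.2.2 specifies both the responder restriction and the log-rank test. The comparison is not a randomized one, but that weakness is in both documents. Removing the test would itself depart from the protocol.
- **That descriptive handling of platelets shows inconsistency.** The SAP says "Duration of platelet transfusion independence will be analyzed descriptively using KM methods", and the protocol planned that too, in a subset dependent on platelet transfusions at baseline.
- **That duration is inflated by 50% or 83%.** Those are the expected maxima of two (1 + 1/2) or three (1 + 1/2 + 1/3) independent, uncensored exponential excesses beyond day 56. They apply only to subjects with exactly two or three runs, a share not given, and to the excess, not to duration. With an assumed mean excess of 30 days, two runs give 56 + 45 = 101 days against 56 + 30 = 86, about 17% more.
- **That the comparison favours oral azacitidine.** The rule applies to both arms. Unequal treatment time is plausible, because continuing past Cycle 6 depends on response or other benefit, but the documents give no treatment time by arm.

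**Conclusion.** The inconsistency is established on the text: the longest-run rule conflicts with the protocol definition, with the SAP's own preceding definition and with SAP 10.2.5, and SAP 16 does not declare it. The direction is firm for each responder: duration stays the same or lengthens. The KM curve is pushed up accordingly, apart from possible local dips caused by intervening censoring, and it comes to depend on time on treatment.

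The size is not known. The rise of about 1% to 78% in the KM median rests entirely on the assumed gap and treatment-time ranges. Distortion of the between-arm test is conditional: with the same transfusion process in both arms, it needs treatment time to differ by arm.

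Duration lies outside the alpha-controlled family (SAP 10.2), and the primary endpoint and OS do not use this rule. The point therefore concerns the accuracy and labelling of secondary results, and should be corrected on that basis.

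**What to change.** - In SAP 10.2.4, make the first qualifying run the main duration analysis. State that this also governs 10.2.6, 10.2.11 and 10.2.13.
- Show the longest run as a labelled supplementary summary.
- Declare in SAP 16 any departure from the protocol definition that is kept.
- Keep the protocol-specified log-rank test among responders if wished, but label it descriptive and give the responder counts beside it.

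The cost is SAP wording and a re-run of the derivation. No new data are needed, because transfusion dates are already collected (protocol 6.7.1). The SAP was signed in March 2019, and the Amendment 6.0 rationale says the primary report was final as of 04-Feb-2020. The practical form now is a supplementary first-run re-analysis with the departure disclosed. Individual durations will be the same or shorter than those under the longest-run rule.

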10.2.5. Time to RBC transfusion independence of ≥ 56 days (8 weeks)

Time to RBC transfusion independence of ≥ 56 days is defined as the time between randomization and the date onset of transfusion independence is first observed (ie, Day 1 of 56 without any RBC transfusions). Subjects who do not achieve RBC transfusion independence

during the treatment period will be censored at the end date of evaluation period which is defined in Section 10.1. In case a subject has more than one rolling periods which meet the independence criteria, the time to the first rolling period will be used in the analysis. Time to RBC transfusion independence curves will be estimated using KM methods and treatment groups will be compared using a stratified log-rank test. A stratified Cox proportional hazards model will be used to estimate the corresponding hazard ratio and 95% CI. Time to RBC transfusion independence (in month) for at least 56 days will also be summarized using descriptive statistics based on subjects who achieve the response.

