10.1. Analysis of Primary Efficacy Endpoint

The primary efficacy endpoint of RBC transfusion independence is defined as the absence of any RBC transfusion during any consecutive "rolling" 56 days within the treatment period. A subject who did not receive any RBC transfusion during a consecutive rolling 56 days (i.e., day 1 to day 56, day 2 to day 57) will be considered as a 56-day RBC transfusion independent responder. Subjects without achieving the response as defined above, subjects with less than 56 days of assessment during the double-blind treatment period, and subjects who had average baseline RBC transfusion units less than 2 units per 28 days (as defined in Section 8.2) will be counted as non-responders.

All RBC transfusion records on or after randomization within the evaluation period will be used to assess the response for each subject. In other words, the days after the end of the evaluation period will not contribute to a rolling period. The end date of the evaluation period is defined as:

- For a subject who discontinues the treatment,

- If the subject doesn't receive a subsequent MDS treatment, use the date of end of treatment visit;
- If the subject receives a subsequent MDS treatment, use the start date of the subsequent MDS treatment – 1 day, or the date of end of treatment visit, whichever is earlier;
- For a subject who is still on-treatment at the time of the database lock for the primary analysis, the subject's latest available assessment date in the database (from AE, vital sign, local and central lab, study drug records, efficacy assessments) will be used.

The 56-day rolling period for the RBS transfusion independent assessment starts on the date of randomization.

Note if the interval between the last RBC transfusion in the evaluation period (if there is at least one RBC transfusion during the evaluation period) and the end date of the evaluation period is less than 56 days, this rolling period, which is less than 56 days, won't be considered as meeting the transfusion independence criteria even though there is no RBC transfusion in it. The day on which the transfusion is received will not contribute to the 56-day without receiving RBC transfusion rolling period.

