10.2.7. Time to RBC transfusion independence of ≥ 84 days (12 weeks)

Time to RBC transfusion independence of ≥ 84 days is defined as the time between randomization and the date onset of transfusion independence is first observed (ie, Day 1 of 84 without any RBC transfusions). The derivation and analysis are similar as for the time to RBC transfusion independence of ≥ 56 days (Section 10.2.5). Time to RBC transfusion independence (in month) for at least 84 days will also be summarized using descriptive statistics based on subjects who achieve the response.

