10.2.14. Time to platelet transfusion independence

Time to platelet transfusion independence is defined as the time between randomization and the first documented date of onset of transfusion independence (ie, Day 1 of 56 without any platelet transfusions). The derivation is similar as for the time to RBC transfusion independence of ≥ 56 days (Section [10.2.5](#)), except using platelet transfusion. Subjects who are platelet transfusion independent at baseline will be excluded from the analysis. Time to platelet transfusion independence will be analyzed descriptively using KM methods. Time to platelet transfusion

independence (in month) for at least 56 days will also be summarized using descriptive statistics based on subjects who achieve the response.

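### Time to transfusion independence is dated from Day 1 of the run but censored at the last evaluation day, so the final 55 or 83 at-risk days can carry no event and the hazard ratio depends on time on treatment

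*SAP*

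**What the plan says.** SAP 10.2.5 measures time from randomization to the date on which independence "is first observed (ie, Day 1 of 56 without any RBC transfusions". If there are several qualifying runs, the first is used. Subjects who never qualify "during the treatment period will be censored at the end date of evaluation period which is defined" in SAP 10.1. The arms are compared by a stratified log-rank test and a stratified Cox model.

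SAP 10.1 ends the evaluation period at the end-of-treatment visit, at the day before subsequent MDS therapy if that is earlier, or at the latest assessment for subjects still on treatment. It adds that "the days after the end of the evaluation period will not contribute to a rolling period", and it counts anyone with under 56 days of assessment as a non-responder.

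The same rule is carried elsewhere:

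- SAP 10.2.7 (84-day RBC endpoint): "The derivation and analysis are similar as for the time to RBC transfusion independence of ≥ 56 days".
- SAP 10.2.14 (platelet endpoint): "The derivation is similar as for the time to RBC transfusion independence of ≥ 56" days.
- SAP 16: the end of the evaluation period "is also used as the censoring date for subjects who do not achieve the corresponding response".

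Protocol 10.6.2.2 has the same structure: non-responders "will be censored at the date of treatment discontinuation or death, whichever occurs first". Neither document moves the censoring date back or dates the event at completion of the run.

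**The concern.** A log-rank or Cox risk set on a given day should hold only subjects who could have an event recorded that day. Here an onset on day t is recorded only if evaluation continues for the rest of the run. A subject who stops on day 40 is already a certain non-responder under SAP 10.1 but counts as at risk for all 40 days.

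This is separate from how death is handled as a competing event, and it persists even if stopping is unrelated to onset. The observed hazard in each arm is scaled down by a factor that depends on how quickly that arm leaves treatment. If the arms leave at different rates, the factors do not cancel.

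A difference is plausible. Protocol 1.4.1 reports an imbalance in deaths, with most azacitidine-arm deaths in the first 56 days on treatment. For a subject whose evaluation ends before day 56, every at-risk day is one on which no event is possible.

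**Working it through.** **Plan's own figure.** The documents state no power, event count or hazard ratio for this endpoint, so there is nothing to reproduce. Treatment durations by arm are not given either, so those below are assumptions.

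**Step 1: days with no possible event.** Let E be the study day on which evaluation ends and W the run length (56 or 84). An onset on day t counts only if t + W − 1 ≤ E, so the latest countable onset is E − 55 or E − 83.

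| E | Last possible onset, 56-day | Empty share | Last possible onset, 84-day | Empty share |
|---|---|---|---|---|
| 364 (12 months) | day 309 | 55/364 = 15% | day 281 | 83/364 = 23% |
| 168 (6 cycles) | day 113 | 55/168 = 33% | day 85 | 83/168 = 49% |
| below W | none | 100% | none | 100% |

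**Step 2: effect on the hazard ratio.** If stopping is independent of onset, then to a close approximation

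observed hazard(t) = true onset hazard(t) × P(E ≥ t + W − 1 | E ≥ t).

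With exponential time on treatment and median m, the second factor is exp(−(W − 1) ln 2 / m). The hazard ratio (azacitidine v placebo; above 1 favours azacitidine) is therefore multiplied by

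exp(−(W − 1) × ln 2 × (1/m_A − 1/m_P)).

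For 90 v 180 days, 1/90 − 1/180 = 0.005556:

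- 56-day: exp(−55 × 0.6931 × 0.005556) = exp(−0.212) = 0.81.
- 84-day: exp(−83 × 0.6931 × 0.005556) = exp(−0.320) = 0.73.

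**Step 3: simulation with a true hazard ratio of 1.** Evaluation time was exponential and capped at about 2 years, with 30,000 to 400,000 subjects per arm. Onset was identical in both arms: either a constant hazard (for example 1/600 or 0.0012 per day), or 40% ever-responders with mean onset at 60 days. The ranges below span the runs. Type I error is for the two-sided 0.05 log-rank test with 108 per arm and 4,000 replicates.

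| Median days, azacitidine v placebo | 56-day HR: formula | simulated | 84-day HR: formula | simulated | Type I error, 56 / 84-day |
|---|---|---|---|---|---|
| 180 v 180 | 1.00 | 1.00 | 1.00 | 1.00 | 0.048 / 0.049 |
| 150 v 180 | 0.96 | 0.94–0.95 | 0.94 | 0.92–0.93 | not run |
| 120 v 180 | 0.90 | 0.89–0.92 | 0.85 | 0.83–0.86 | 0.062 / 0.082 |
| 90 v 180 | 0.81 | 0.80–0.81 | 0.73 | 0.71–0.73 | 0.097 / 0.161 |
| 180 v 120 | 1.11 | 1.08–1.13 | 1.17 | 1.18–1.19 | not run |

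With a true hazard ratio of 2 and medians of 90 v 180, the rule as written gives 1.59 (56-day) and 1.41 (84-day).

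**Step 4: with the dates aligned.** Censoring non-responders at E − 55 or E − 83, or dating the event at Day 56 or Day 84 and keeping E, gave identical hazard ratios. With a true value of 1 these were 0.97–1.03 in the smaller runs and 0.99–1.01 in the larger. With a true value of 2 they were 1.99–2.01. Type I error was 0.047–0.053.

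**The case against.** The mechanism is not in dispute. The case against concerns its size and the remedy.

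- **Size.** The larger figures need azacitidine's median time on treatment to be half of placebo's throughout. Protocol 1.4.1 describes only an early cluster and gives no counts. With a median of 180 days in both arms plus 5% to 15% of azacitidine subjects stopping in days 1–56, the as-written hazard ratio was 0.93–1.00 (56-day) and 0.95–0.98 (84-day). That is about 1–7% away from the realigned result, with Monte Carlo error near 2%. This stands as a limit on size.
- **Direction.** The one documented difference pushes against azacitidine, which is conservative for a superiority claim. This also stands; no passage shows placebo subjects stopping earlier.
- **Estimand.** An arm that loses more subjects early does have fewer completed responses under SAP 10.1, so part of the shift is a real difference in the endpoint as defined. That difference already appears in the primary responder proportion. Censoring at E does not turn the hazard ratio into a clean composite of onset and staying on treatment.
- **Remedy.** Moving the censoring date back leaves subjects with under 56 days no at-risk time. In the early-cluster runs that was 23–31% of azacitidine v 19% of placebo subjects (56-day), and 31–39% v 27–28% (84-day). Nor does realignment cure informative stopping, since lack of efficacy and progression are reasons to discontinue (Protocol 12). Both points are true and should be stated with the result. Neither justifies counting days on which no event can occur.
- **Scope.** These are secondary analyses outside alpha control (SAP 10.2), and the platelet endpoint is descriptive Kaplan-Meier only.

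**Conclusion.** The concern holds. The counts of 55 and 83 empty days are exact and follow from SAP 10.1, 10.2.5 and 10.2.7. The size of the bias rests on assumed durations and on stopping that is independent of onset. The null hazard ratio is undistorted if the arms stay on treatment equally long and moves by about 1–7% under a modest early cluster of azacitidine exits. It falls to about 0.90 / 0.85 (56-day / 84-day) at medians of 120 v 180 days and to about 0.81 / 0.72 at 90 v 180. If placebo subjects leave earlier, the bias reverses in favour of azacitidine.

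Even with equal durations, the Kaplan-Meier curves for time to independence are too low; for the platelet endpoint that is the only effect. The primary responder proportion and OS are untouched. The rule should be corrected because it can give a wrong hazard ratio and p-value, but the trial's main conclusion does not turn on it.

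**What to change.** Change the censoring sentence in SAP 10.2.5 in one of two ways:

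1. Keep the Day 1 event date. Censor non-responders at the last day on which an onset could have been observed: end of evaluation minus 55 days for the 56-day RBC and platelet endpoints, minus 83 days for the 84-day RBC endpoint, and no earlier than randomization.
2. Keep the censoring date. Date the event at Day 56 or Day 84 of the run, when the criterion is met, and report Day 1 onset only descriptively in responders, a summary the SAP already plans.

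Both give the same hazard ratio. The second leaves short-stay subjects with at-risk time in the ITT data set, though only before any event is possible. Make matching edits in SAP 10.2.7, 10.2.14 and 16. Report by arm the number of subjects with under 56 and under 84 days of evaluation, and note that realignment does not address informative stopping.

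The cost is one SAP sentence and one derived date, with no new data. The rationale for Protocol Amendment 6.0 says the primary clinical study report is already final, so for this trial the corrected analysis would be a supplementary one on existing data.
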